### 3.3. Assessment of resources

The study will be conducted as a collaboration between the Department of Health Promotion, the Department of Endocrinology and the Center for Gender Identity, Aalborg University Hospital. Patients will be recruited at the Center for Gender Identity, BIA measurements will be performed at the Department of Health Promotion, and the DXA scans at the Department of Endocrinology by experienced personnel. The recruitment is directed by leading physician [name] at the Center for Gender Identity. She will be

responsible for instructing the nurses at the outpatient clinic which see patients for follow-up as a part of their treatment plan. Data collection is done by clinical manager and primary investigator [name] from the Department of Health Promotion who will contact the patients if they are interested in participating, collect their written consent, and meet the patients at the hospital for the data collection regarding BIA-measurements and demographics. [name] from the Department of Endocrinology are responsible for the DXA-scans.

### 3.4. Study procedures

Patients are recruited at their consultation with the nurse at the Center for Gender Identity at Aalborg University Hospital. The consultation is part of the patient's treatment plan. Patients will be given information regarding the study, and if interested, they will be provided with a form to fill out with their contact information, so they can be contacted by the investigators. Should the patient agree to be contacted via telephone or e-mail, they will be given instruction regarding their rights as a participant in a scientific study ("*Dine rettigheder som forsøgsperson i et sundhedsvidenskabeligt forskningsprojekt*") as well as written material specifically pertaining to the study ("*Deltagerinformation*"). Should the subject be deemed fit for the study, based on the in- and exclusion criteria, contact will be made via phone or e-mail and they will receive further information regarding the study, and invited to a personal meeting the principal investigators office at the Department of Health Promotion. Here, the conversation can be undisturbed and details of the study procedures will be outlined. In advance, the subject will be informed of the opportunity to bring a relative or a representative to the meeting. At the meeting, the patient and any representative will be informed of the 24-hour deliberation period before providing informed consent, but if the patient agrees to participate, they will sign the informed consent form at the meeting and receive a copy of the signed form to take home. If they wish for time to deliberate, they can come by the principal investigators office another day to sign the form. No study procedures will be performed until the informed consent form has been signed by both the participant and the investigator. The signed consent form will give the principal investigator direct access to collect information from participants Electronic Patient Journal (EPJ) which are necessary to complete the study.

After providing informed consent, the participant will undergo the study procedures. Body composition will be analyzed by BIA-measurement and DXA scans. Data will be analyzed using relevant statistical analyses and presented as a cross-sectional study.

#### 3.4.1. Whole body dual X-ray absorptiometry (DXA) scan

Through whole body DXA scans, we will obtain information regarding body composition. The effective radiation dose for one whole body DXA scan has been found to be between 0,001 and 0,01 mSv.

Estimated time: 30 min.

### 3.4.2. Bioelectrical impedance analysis (BIA)

In each patient body composition is measured using the “male” and “female” setting of the Tanita MC-780 MA, respectively. BIA-measurements take less than 1 minute, are without any side effects, and a part of standard care in this patient group when assigned for weight loss therapy at the Department of Health Promotion.

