## 2.2. Objectives

Hypotheses:

- By optimizing the use of sex specific reference values, we can improve the precision of the estimation of body fat volume using BIA measurements in trans gender males.

Aim:

- To assess body composition of trans gender males in hormonal therapy using BIA compared to DXA.
- To investigate whether binary reference values using BIA measurements in trans gender males in hormonal therapy is reliable – and thereby if BIA maybe a useful tool for assessing whether a trans gender man is suitable for mastectomy.

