## 4. Data collection

Following the participants’ informed consent, data regarding age, sex, medication, onset of hormonal therapy, and blood samples (p-alanine transaminase, p-albumin, p-alkaline phosphatase, p-bilirubin, B-erythrocytes, B-hemoglobin, p-estradiol, p-follicle stimulating hormone, Hb(B)-hemoglobin A1c, p-cholesterol (LDL), B-leucocytes, B-erythrocyte volume (MCV), p-prolactin, p-sex hormone binding globulin, p-testosterone, p-free testosterone, p-thyroid screening, B-thrombocytes, p-lutropin will be collected from the participants’ EPJ. The information gathered is for use in the research project only.

The participants will be measured on the BIA scale twice and once with DXA and they will be asked questions about their habits concerning smoking and exercise. The center for Gender Identity regularly refers trans gender persons to the Department of Health Promotion for weight loss therapy. Patients at the Department of Health Promotion are routinely weighed on the Tanita MC-780 MA-scale. The blood samples collected in this study are routine samples and collected as a part of the participants treatment plan. DXA scans are not standard procedure in this patient group and is the only part of this project which is not part of the patient’s regular treatment plan.

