## 5. Data analysis

### 5.1. Statistical methods

#### 5.1.1. Sample size

In this study we aim to include 10 participants. It was not possible to conduct a sample size calculation based on the reference data on the Tanita MC-780 MA-scale, as Tanita will not share their data or information about their population. We have a vast experience with DXA scans in the clinic, and from this

experience we know that 10 persons will be enough to detect a difference in body composition in a pilot study.

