#### 5.1.2. Statistical methods

Student's unpaired t tests will be used to compare variables between groups. Correlation analyses will be performed using Pearson's correlation coefficient. Wilcoxon rank-sum test will be used to compare nonparametric data between groups. Fischer's exact test will be used to test differences in cross tables.

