#### 5.1.3. Statistical significance

We use a statistical significance level of  $\alpha < 0,05$ .

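### Each participant is read on both BIA settings and by DXA, but the methods fixed in Section 5.1.2 never form an error against DXA and, as planned, do not compare the two settings' errors

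*Protocol*

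**What the plan says.** Protocol Section 3.4.2: "In each patient body composition is measured using the" male setting and the female setting of one BIA device. Section 4 confirms the count: "The participants will be measured on the BIA scale twice and once with DXA".

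Section 2.2 gives the purpose. The hypothesis is that better use of the sex-specific references makes the BIA estimate of body fat more precise. The second aim is "To investigate whether binary reference values using BIA measurements in trans gender males in hormonal therapy is reliable", and from that whether BIA may help in judging suitability for mastectomy.

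Section 5.1.2 is a short list of methods. Student's "unpaired t tests will be used to compare variables between groups"; the Wilcoxon rank-sum test serves non-parametric data; "Correlation analyses will be performed using Pearson's correlation coefficient"; Fisher's exact test serves cross tables. The groups and variables are not named. The two settings are not mentioned again after Section 3.4.2, and no difference from DXA is defined anywhere.

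On size, Section 5.1.1 says "In this study we aim to include 10 participants" and gives clinical experience as the basis. Section 7 concedes that the cohort is too small to improve the reference values, but still expects the data to show whether BIA is useful in this population.

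**The concern.** Reading the same person on both settings and by DXA gives two errors per person, one for each binary reference. Those errors, and the contrast between them, bear directly on the hypothesis and the second aim. The listed methods produce neither. An analyst who follows Section 5.1.2 can report that the two equations give different values, that each correlates with DXA, and that a mean does or does not differ significantly from the DXA mean. None of these says how far a setting is off in an individual, or whether one setting is closer to DXA than the other.

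Two biased settings could therefore both pass as compatible with DXA, in a study whose results are expected (Section 8.3) to inform weight-loss treatment and referral for surgery.

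**Working it through.** **Inputs from the protocol.** n = 10 (5.1.1); significance level 0.05, sidedness not stated and taken as two-sided (5.1.3); two BIA readings and one DXA per person (4). The sample size has no effect size, SD or power behind it, only the statement that from "experience we know that 10 persons will be enough to detect a difference in body composition in a pilot study", so there is no figure to reproduce. The only BIA error in the document is in Section 2.1.2: mean 12.4 kg, SD 6.2 kg, for fat-free mass against MRI in cancer patients. All other values below are assumptions.

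**1. Male against female readings.** With M, F and D for the male setting, female setting and DXA, (M − D) − (F − D) = M − F. DXA drops out. Take biases in fat percentage points of (−5, +1) and (−3, +3). In the first the female setting is closer; in the second they tie. M − F averages −6 in both. With a between-person SD of 5, shared error SD 3 and setting-specific SD 1.5, the unpaired test of M against F was significant in 65% and 64% of simulated studies. It cannot tell the two situations apart.

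**2. Pearson's r.** corr(M + c, D) = corr(M, D) for any constant c. Let the error SD be 1 and s the between-person SD, both in error SDs, with error independent of D. Then r = s/√(s² + 1), which is 0.71 for s = 1 and 0.89 for s = 2 whatever the bias (simulated means at n = 10: about 0.69 and 0.88). With biases of −5 and +1, simulated r for the two settings agreed within 0.01.

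**3. Each setting against DXA, unpaired.** This assumes that the unnamed groups are the readings of a setting and of DXA. DXA has variance s² and the BIA reading s² + 1, so SE = √((2s² + 1)/10).
- s = 1: SE = √0.3 = 0.548; with t(18) = 2.101, the observed mean difference must exceed roughly 1.15 error SDs.
- s = 2: SE = √0.9 = 0.949; it must exceed roughly 1.99 error SDs.
- Paired, for comparison: SE = 1/√10 = 0.316; with t(9) = 2.262, the threshold is about 0.72.

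Simulation (40,000 runs per scenario; biases +b and −b with b = 0.5 to 0.8; error correlation 0.5 to 0.95; s = 1 or 2): neither unpaired test was significant in 0.60 to 0.996 of studies.

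**4. Larger biases.** In the percentage-point simulation the error SD is √(3² + 1.5²) = 3.35. With a between-person SD of 5 points (5/3.35 = 1.49 error SDs), a bias of 3 points (0.89 error SD) was detected by the unpaired test in 9% of studies and a bias of 5 points (1.49 error SDs) in 49%. With a between-person SD of 9, the 5-point bias was detected in 5%. So the miss rate falls with bias, more slowly when participants vary more.

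**5. What the missing analysis could deliver.** At n = 10 a paired comparison has 80% power for a difference of about 1.0 SD of the paired differences. Where the simulated settings truly differed in absolute error, with biases (−5, +1) or (−1, +4), power was 14% to 41%. Where they tied, false separation was about 5%. Using the 6.2 kg SD purely for scale:
- CI of the bias: ±2.262 × 6.2/√10 = ±4.4 kg.
- Limits of agreement: bias ±1.96 × 6.2 = ±12.2 kg.
- CI of each limit: ±2.262 × 6.2 × √(3/10) = ±7.7 kg.

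**The case against.** **The question is partly inferred.** No section names a choice of setting as an output. Section 2.2 asks about reliability, and both settings could prove unreliable without being ranked. Section 7 narrows the goal further. This stands: a reader might infer that the study is meant to recommend a setting, and the document does not say so. But the hypothesis about making better use of the sex-specific references, together with the double reading, does call for each setting's error against DXA.

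**It could be left to an analysis plan.** The exact contrast could be. But Section 5.1.2 does not defer; it fixes a list, and carrying out that list would not address the aim.

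**The data permit the analysis.** True. A reader might conclude that the trial cannot say which setting is closer. That goes too far: the paired data are collected, and each setting's mean difference from DXA can be read descriptively. The supported statement is that the plan does not make the comparison.

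**The simulated biases are chosen.** Also true. Nothing in the protocol supports 0.5 to 0.8 error SD. The one cited error, 12.4/6.2 = 2.0 SD, lies well outside that range, though for another quantity, reference method and population.

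**Absolute error is an imperfect yardstick.** It mixes scatter with a constant offset, which Section 2.1.2 regards as correctable. This stands, and is why bias and limits of agreement belong in the fix.

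**Conclusion.** The point holds as a mismatch between design and analysis: within-person readings on two settings and DXA are collected, and none of the fixed methods forms an error against DXA or compares the settings' errors. This part rests on reading the sections together and on two algebraic facts, not on simulation.

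The size is conditional. The figure of about 60% to 99% of studies with neither biased setting significant assumes unpaired tests of each setting against DXA, biases of 0.5 to 0.8 error SD and a between-person SD of 1 to 2 error SDs. It falls at larger biases.

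A stronger claim is tempting: that two equally wrong settings would often be reported as one good and one bad. With one paired test per setting, exactly one is significant in 49% to 69% of studies over the same bias range. The protocol plans neither paired tests nor a rule that ranks settings by significance. The figure also depends on the bias: 7% to 10% at 0.1 SD, 36% to 38% at 1 SD and about 0% at 2 SD. It should not be held against this plan. It does show that making the tests paired would not by itself supply the comparison.

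**What to change.** Add to Section 5.1.2, for body fat percentage:

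- For each participant and each setting, compute the error as the setting's reading minus DXA.
- For each setting, report the mean bias and the limits of agreement, with 95% confidence intervals.
- For each participant, compute the absolute error on the male setting minus the absolute error on the female setting. Report the mean (or median) of this paired difference with a 95% confidence interval.
- Base any statement about which setting is closer to DXA on that paired interval, presented as estimation and not as a significance test, and read it beside the two biases so that a constant offset is not mistaken for scatter.

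The cost is one added analysis on readings already planned, with no extra burden on participants. The drawback is precision: with 10 people the interval will be wide and the comparison often inconclusive (power roughly 15% to 40% for moderate differences, under the assumptions above). The protocol should say so in advance.

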## 4. Data collection

Following the participants’ informed consent, data regarding age, sex, medication, onset of hormonal therapy, and blood samples (p-alanine transaminase, p-albumin, p-alkaline phosphatase, p-bilirubin, B-erythrocytes, B-hemoglobin, p-estradiol, p-follicle stimulating hormone, Hb(B)-hemoglobin A1c, p-cholesterol (LDL), B-leucocytes, B-erythrocyte volume (MCV), p-prolactin, p-sex hormone binding globulin, p-testosterone, p-free testosterone, p-thyroid screening, B-thrombocytes, p-lutropin will be collected from the participants’ EPJ. The information gathered is for use in the research project only.

The participants will be measured on the BIA scale twice and once with DXA and they will be asked questions about their habits concerning smoking and exercise. The center for Gender Identity regularly refers trans gender persons to the Department of Health Promotion for weight loss therapy. Patients at the Department of Health Promotion are routinely weighed on the Tanita MC-780 MA-scale. The blood samples collected in this study are routine samples and collected as a part of the participants treatment plan. DXA scans are not standard procedure in this patient group and is the only part of this project which is not part of the patient’s regular treatment plan.

## 5. Data analysis

### 5.1. Statistical methods

#### 5.1.1. Sample size

In this study we aim to include 10 participants. It was not possible to conduct a sample size calculation based on the reference data on the Tanita MC-780 MA-scale, as Tanita will not share their data or information about their population. We have a vast experience with DXA scans in the clinic, and from this

experience we know that 10 persons will be enough to detect a difference in body composition in a pilot study.

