## 3. Methods

### 3.1. Study design

This pilot study will be performed as a cross-sectional study. There are currently no plans of a larger scale follow-up study. In case of a follow-up study a second application will be sent.

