## 7. Study limitations

In this study we use a small cohort, and therefore we do not have the statistical foundation to be able to improve the sex specific reference values of BIA measurements, but we can use the data to assess body composition of trans gender males in hormonal therapy using BIA compared to DXA, and thereby assess whether BIA is a useful tool for assessing body composition in trans gender males. Furthermore, we aim to use these data for further hypothesis generation.

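### Section 5.1.1 states without a difference, SD or power that 10 people suffice, and section 5.1.2 names only independent-sample tests of location for what is a within-person comparison

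*Protocol*

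**What the plan says.** Protocol section 5.1.1 aims for 10 participants. It explains that no calculation could be based on the scale manufacturer's reference data, because these are not shared. It then relies on experience with DXA to state that "10 persons will be enough to detect a difference in body composition in a pilot study". Section 5.1.3 adds a significance level of 0.05 and nothing on sidedness.

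The measurements are repeated within the same people. Section 3.4.2: "In each patient body composition is measured using the" male and the female setting of the device. Section 4: "The participants will be measured on the BIA scale twice and once with DXA".

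For the analysis, section 5.1.2 says that "unpaired t tests will be used to compare variables between groups" and that a "Wilcoxon rank-sum test will be used to compare nonparametric data between groups". It also names Pearson correlation and Fisher's exact test. It names no paired test, and the protocol defines no groups.

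Section 3.1 describes the work as a pilot: "This pilot study will be performed as a cross-sectional study". Section 7 concedes a small cohort and says "we aim to use these data for further hypothesis generation". It also says the data will serve to "assess whether BIA is a useful tool for assessing body composition in trans gender males".

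**The concern.** There are two linked problems.

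First, the sufficiency statement cannot be checked, because it has no inputs apart from alpha. The basis offered is also of the wrong kind. The aim in section 2.2 is to compare BIA with DXA, so the relevant spread is that of the within-person differences between the methods. Knowing how DXA behaves does not give that spread. The manufacturer's reference data are not what is needed for it either.

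Second, the tests named do not match the data. An unpaired test treats the BIA and DXA readings of one person as if they came from two unrelated people. Readings of the same quantity in the same person should be positively correlated. The unpaired standard error is then too large, the test is conservative, and power is lost.

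Section 7 intends to judge the usefulness of BIA from these data, and section 2.2 links that judgement to suitability for mastectomy. A test that misses a real bias would make BIA look better than it is.

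**Working it through.** **The plan's own figure.** The number 10 cannot be reproduced. Alpha is the only input given.

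**Inputs.** n = 10 (section 5.1.1) and alpha = 0.05 (section 5.1.3). Two-sided testing is assumed. Let d be the mean BIA-DXA difference divided by the SD of the within-person differences.

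**Paired t test.** Power is the probability that a noncentral t variable with 9 df and noncentrality d√10 exceeds t(0.975, 9) = 2.262. The opposite tail is negligible.

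| d | d√10 | Power |
|---|---|---|
| 0.5 (illustrative) | 1.58 | 29% |
| 1.0 | 3.16 | 80% |
| 2.0 | 6.32 | over 99.9% |

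Power of 80% is reached at d = 0.996.

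**Precision of the mean difference.** The 95% CI half-width is 2.262/√10 = 0.715 SD of the differences. Section 2.1.2 cites a study with the same device in which BIA overestimated fat-free mass by a mean of 12.4 kg, SD 6.2. Its reference was thigh MRI and its patients had colorectal cancer, so it is only a proxy. Treating 6.2 kg as the SD of paired differences is an assumption.

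- SD 6.2 kg: half-width 0.715 × 6.2 = 4.4 kg; 80% power at 0.996 × 6.2 = 6.2 kg
- SD 4 kg (assumed): half-width 0.715 × 4 = 2.9 kg
- SD 2 kg (assumed): half-width 0.715 × 2 = 1.4 kg

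The cited bias is 12.4/6.2 = 2.0 SD, which a paired test on 10 people would almost certainly detect.

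**Unpaired t test on the same data.** With equal SDs and within-person correlation ρ, the true variance of the mean difference is 2σ²(1−ρ)/n. The unpaired test estimates 2σ²/n, so its standard error is too large by a factor 1/√(1−ρ): 1.41, 2.24 and 3.16 at ρ = 0.5, 0.8 and 0.9. The correlations are assumed. Type I error and power come from 400,000 simulated bivariate normal trials per setting. The CI half-width, with SDs taken as known, is t(0.975, 18) × √(2/10)/√(2(1−ρ)), where t(0.975, 18) = 2.101.

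| | Paired t | Unpaired, ρ = 0.5 | Unpaired, ρ = 0.8 | Unpaired, ρ = 0.9 |
|---|---|---|---|---|
| Type I error | 5% | 0.9% | 0.05% | below 0.01% |
| Power at 1 SD | 80% | 59% | 15% | 3% |
| Power at 2 SD | over 99.9% | 99.8% | 89% | 48% |
| 95% CI half-width (SD of differences) | 0.72 | 0.94 | 1.49 | 2.10 |

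**Rank tests** (exact critical values, 40,000 simulations, shift of 1 SD). The rank-sum test has 53%, 14% and 3% power at the three correlations. The signed-rank test has about 79% at each.

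**The case against.** The protocol is candid. It says no calculation was possible, limits its claim to a pilot, concedes a small cohort and aims at generating hypotheses. No stated figure is wrong, and on the only bias and SD it cites (ratio 2.0) ten paired observations are ample. This stands in part: 10 has not been shown to be too few, and a small pilot needs no power calculation. It does not support a statement that 10 is known to be enough. Section 7's concession also limits only the improvement of reference values, not the comparison of BIA with DXA.

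Section 5.1.2 does not expressly assign the unpaired tests to BIA versus DXA. Data on smoking, exercise and medication are collected, so the tests could be meant for subgroups, and a separate analysis plan could name a paired test. That reading is possible. But the protocol defines no subgroups, and the reading would leave its stated aim without any named test of location that fits the data. A reader following the text would use the tests it names.

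The size of the loss depends on assumed correlations and equal variances. At a 2 SD bias it is slight at ρ = 0.5, moderate at 0.8 and serious only at 0.9. This stands, and it is why the results are shown as a range.

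**Conclusion.** The concern holds, as a minor one. The sufficiency statement has no basis in the document, and the named tests of location do not suit paired measurements.

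The choice of test matters more. At a bias of 1 SD of the differences, power falls from 80% to between 59% and 3% over the assumed correlations of 0.5 to 0.9. With a paired analysis, 10 people show a large bias reliably but not a moderate one.

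These figures assume two-sided testing, normal data and, for the unpaired comparison, equal variances. The kilogram values also depend on a proxy or assumed SD.

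**What to change.** Keep 10 participants and change two places in the protocol.

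1. **Section 5.1.2**, add: *Each BIA setting will be compared with DXA within participants by a paired t test, or by the Wilcoxon signed-rank test for nonparametric data.* If the unpaired and rank-sum tests are meant for subgroups of participants, say so there.
2. **Section 5.1.1**, replace the sufficiency sentence with: *Ten participants is a pilot number that does not rest on a power calculation. With a paired analysis it gives a 95% CI for the mean BIA-DXA difference of about ±0.72 SD of the within-person differences, and 80% power (two-sided 0.05) for a mean difference of about 1 SD. A non-significant difference is not evidence of agreement.*

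Limits of agreement would be a useful addition, since a paired test addresses mean bias only. With 10 people the 95% CI half-width of each limit is about 2.262 × √(1/10 + 1.96²/18) = 1.27 SD of the differences.

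The cost is a few sentences, with no extra participants or measurements. The one drawback is that the protocol will describe its capability less favourably.
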